8.3 Safety Assessments

Details regarding specific safety procedures/assessments to be performed in this study are provided below. The total amount of blood to be drawn over the course of the study (from

pre-study to post-study visits), including approximate blood volumes drawn by visit and by sample type per participant, can be found in the central laboratory manual.

Planned time points for all safety assessments are provided in the SoA.

8.3.1 Physical and Neurological Examinations

A complete physical examination, including a neurological examination, will be conducted at the visits specified in the SoA, per institutional standard. The investigator (or qualified designee, consistent with local requirements) will perform the examinations of the following organ systems:

- Head, eyes, ears, nose, and throat
- Neck
- Respiratory system
- Cardiovascular system
- Abdomen
- Skin and extremities
- General appearance
- Neurological system (see Appendix 8)

Height and weight will also be measured and recorded (Section 8.3.3).

Investigators should pay special attention to clinical signs related to previous serious illnesses. Any medical conditions found during the physical and neurological examinations will be recorded in the Sponsor database.

8.3.2 Vital Signs

Vital signs will be measured in a semi-supine position after 5 minutes of rest and will include temperature, blood pressure, pulse rate, and respiratory rate.

It is recommended that individual sites use the same method for measuring temperature (eg, oral, tympanic) in all participants throughout the study.

For blood pressure readings, the correct size of the blood pressure cuff and correct positioning on the participant's arm is essential for accurate measurements. It is recommended that individual sites use the same method (manual or automated) for measuring blood pressure and pulse throughout the study.

8.3.3 Height/Weight

Height (inches/centimeter) will be measured and recorded at the visits specified in the SoA. Measurements should be rounded to the nearest inch/centimeter (without shoes).

Body weight will be measured using a standardized scale (provided by the Sponsor if requested) and should be rounded to the nearest pound/kilogram. Participants' weight should be measured after voiding and while wearing light clothing (eg, no coats or heavy sweatshirts). The site should follow their local procedures to ensure the body weight scale is working properly.

8.3.4 ECGs

Twelve-lead ECGs will be performed when the participant is in the supine position after 5 to 10 minutes of rest using a central ECG machine that automatically calculates heart rate and measures PR, QRS, QT, and QTcF intervals according to the instructions in a separate ECG instruction manual. Cardiologist overread will be provided by the central ECG vendor.

All scheduled ECGs will be performed in triplicate. ECG measurements should be obtained in close succession; ie, less than 2 minutes apart with all 3 measurements completed in less than 4 minutes.

At Visit 1 (Screening), the average of the 3 QTcF intervals based on the central vendor overread will be used to assess eligibility. At Visit 4 (Day 1), the average of the 3 QTcF intervals based on the local ECG printout will be used to assess eligibility (Section 5.2).

During the double-blind treatment period, participants will discontinue study intervention if the average of the 3 QTcF intervals at a visit is either >500 msec or increases by >60 msec relative to Visit 4 (Day 1). Details on discontinuation of study intervention due to QTcF results are in Section 7.1.

If ECG assessments were missed entirely at the scheduled visit during treatment or if all ECGs at a visit were invalid due to technical issues, the ECG should be obtained at the next scheduled visit.

8.3.5 Alcohol Screen (Breathalyzer)

An alcohol breath test will be performed at Visit 1 (Screening) and Visit 4 (Day 1). Participants must have a negative alcohol breath test at both visits to be eligible for the study (Section 5.2). A breathalyzer will be provided to each site by the Sponsor.

8.3.6 Clinical Safety Laboratory Assessments

Refer to Appendix 2 for the list of clinical laboratory tests to be performed and to the SoA for the timing and frequency.

The investigator or medically qualified designee (consistent with local requirements) must review the laboratory report, document this review, and record any clinically relevant

changes occurring during the study in the AE section of the CRF. The laboratory reports must be filed with the source documents. Clinically significant abnormal laboratory findings are those which are not associated with the underlying disease, unless judged by the investigator to be more severe than expected for the participant's condition.

All protocol-required laboratory assessments, as defined in Appendix 2, must be conducted in accordance with the laboratory manual and the SoA.

If laboratory values from nonprotocol-specified laboratory assessments performed at the institution's local laboratory require a change in study participant management or are considered clinically significant by the investigator (eg, SAE or AE or dose modification), then the results must be recorded in the appropriate CRF (eg, SLAB).

For any laboratory tests with values considered clinically significantly abnormal during participation in the study or within 14 days after the last dose of study intervention or through completion of Visit 10, whichever is later, every attempt should be made to perform repeat assessments until the values return to normal or baseline or if a new baseline is established as determined by the investigator.

8.3.6.1 Confirmation of Postmenopausal State

Female participants whose postmenopausal status is in question are required to have 2 pretreatment FSH measurements (approximately 2 weeks apart with a minimum interval of 10 days) in the postmenopausal range (Appendix 5). The first FSH measurement will be obtained at Visit 1 (Screening). Participants whose first FSH measurement is in the postmenopausal range, but who cannot have a second measurement within approximately 2 weeks of Visit 1 (Screening), should be excluded. These participants may be rescreened after consulting with the Sponsor.

8.3.6.2 Pregnancy Testing

General Guidance

Pregnancy testing will be performed as specified in the SoA and is not required during a Down-titration Visit.

During the screening period (pre-randomization):

- If urine test is positive, a serum pregnancy test is required to confirm or dismiss the initial result. The participant should be excluded unless a negative status is confirmed by 2 negative serum pregnancy tests performed approximately 24 hours apart.
- If a urine test cannot be confirmed as negative (eg, an ambiguous result), a serum pregnancy test is required and must be negative to proceed to randomization. The participant must be excluded from participation if the serum pregnancy result is positive.

During the treatment and follow-up period:

- If urine test is positive, a serum pregnancy test is required. Study intervention should be held until a negative status is confirmed by 2 negative serum pregnancy tests performed approximately 24 hours apart.
- If a urine test cannot be confirmed as negative (eg, an ambiguous result), a serum pregnancy test is required. Study intervention should be held until a negative serum pregnancy test is obtained.
- Participants with a positive serum pregnancy test (or positive urine test and participant refuses the required follow-up serum test) must be discontinued from study intervention and followed as specified in Section 7.1.

Local serum tests may be performed in the event that the central laboratory results would not be available in time for prompt decision making.

Participants should not take products containing high-dose biotin (>5 mg/day) 1 day before and on the day of pregnancy testing as this might interfere with the results of the test.

WOCBP

All WOCBP (see Section 10.5.1 for definition) participating in the study will have a highly sensitive local urine pregnancy test AND serum pregnancy test at the visits indicated in the SoA and when pregnancy is suspected. A negative pregnancy test is required immediately (ie, on the same day) before dosing at each scheduled visit.

WONCBP

All WONCBP (see Section 10.5.1 for definition) participating in the study will have a highly sensitive urine pregnancy test at Visits 1, 4, and 8.

8.3.7 Suicidal Ideation and Behavior Monitoring

8.3.7.1 Clinical Assessments for Suicidal Ideation and Behavior Monitoring

Suicidal ideation and behavior will be prospectively assessed during this study using the C-SSRS. The C-SSRS should be administered by trained raters at specified time points, as specified in the SoA, as well as at unscheduled visits as clinically indicated. Site staff should review the contents of the C-SSRS for completeness.

If the C-SSRS is administered by someone other than the investigator, consider providing the completed C-SSRS to the investigator for review, prior to their assessment of the participant and to further inform their evaluation.

The C-SSRS is not explicit about whether the participant specifically has ideation at the time of screening. If a participant reports a prior history of ideation/behavior, the assessor should also inquire and document if this is also present at the time of the screening visit.

PRODUCT: MK-1942

PROTOCOL/AMENDMENT NO.: 006-03

Participants who at any time during this study report suicidal ideation or behavior that is considered to be an AE, either between visits or during visit interviews, must be assessed by the investigator. Participants who report suicidal ideation with intent, with or without a plan or method (ie, a positive response to items 4 or 5 in the assessment of suicidal ideation on the C-SSRS) or suicidal behavior must be evaluated that day by a psychiatrist or other trained mental health professional who is a licensed psychologist, social worker, or mental health nurse practitioner (or comparable professional qualification in countries outside the United States). After that evaluation, only those participants whose suicidal ideation is considered by the evaluator to be passive, and who expressly deny any intent to act, and who, after evaluation, are not judged to be at serious risk for self-harm during the course of the study may continue in the study; other participants must be discontinued from study participation and receive appropriate clinical follow-up care to ensure their safety. In addition, all AEs of suicidal ideation or behavior must be recorded as an ECI (Section 8.4.7). Sites are to designate which health care professionals are to be responsible for acute care on-site and to specify referral center(s) to be used for further evaluation.

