7 DISCONTINUATION OF STUDY INTERVENTION AND PARTICIPANT WITHDRAWAL

7.1 Discontinuation of Study Intervention

Discontinuation of study intervention does not represent withdrawal from the study.

As certain data on clinical events beyond study intervention discontinuation may be important to the study, they must be collected through the participant's last scheduled follow-up, even if the participant has discontinued study intervention. Therefore, all participants who discontinue study intervention prior to completion of the protocol-specified treatment period will still continue to participate in the study as specified in Section 1.3 and Section 8.11.6.

Participants may discontinue study intervention at any time for any reason or be discontinued from the study intervention at the discretion of the investigator should any untoward effect occur. In addition, a participant may be discontinued from study intervention by the investigator or the Sponsor if study intervention is inappropriate, the study plan is violated, or for administrative and/or other safety reasons. Specific details regarding procedures to be performed at study intervention discontinuation are provided in Section 1.3 and Section 8.11.5.

A participant must be discontinued from study intervention but continue to be monitored in the study for any of the following reasons:

- The participant or participant's legally acceptable representative requests to discontinue study intervention.
- The participant's treatment assignment has been unblinded by the investigator, MSD subsidiary, or through the emergency unblinding call center.

- The participant has a medical condition or personal circumstance which, in the opinion of the investigator and/or Sponsor, place the participant at unnecessary risk from continued administration of study intervention.
- The participant has a positive urine or serum pregnancy test. See Section 8.3.6.2 for pregnancy testing requirements.
- The participant has an ALT $\ge 3x$ ULN
- The participant has an AST $\geq 3x$ ULN with total bilirubin $\geq 2x$ ULN and ALP $\leq 2x$ ULN
- The participant has an AST $\ge 3x$ ULN with ALT value ≥ 100 IU/L

Note 1: Liver function tests are to be confirmed by repeat testing within 48 hours of initial test results. If test results are unable to be confirmed within this timeframe, the study intervention should be withheld until test results are available. Study intervention should be discontinued if unable to repeat testing.

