Note 2: If the investigator identifies a clear cause for the liver enzyme elevations unrelated to study intervention, then study intervention may be continued with approval by the Sponsor.

- The participant meets either of the following criteria for QTcF interval at a visit (**Note**: ECGs will be performed in triplicate [Section 8.3.4]):
 - The average of the 3 QTcF intervals based on either the local ECG printout or subsequent central vendor overread is >500 msec.
 - The average of the 3 QTcF intervals based on either the local ECG printout or subsequent central vendor overread increased by >60 msec, relative to the central vendor overread average at Visit 4 (Day 1).
- The participant reports suicidal ideation with intent, with or without a plan or method through an AE or C-SSRS (ie, a positive response to Items 4 or 5 in the assessment of suicidal ideation on the C-SSRS) or suicidal behavior. If the reported suicidal ideation is passive, and participant expressly denies any intent to act, and who, after evaluation, is not judged to be at serious risk for self-harm during the study, the participant may continue on study intervention. Refer to Sections 8.3.7.1 on Clinical Assessments for Suicidal Ideation and Behavior Monitoring (for requirements pertaining to the evaluation of such events), and Section 8.4.7 for Events of Clinical Interest.
- The participant is unable to tolerate treatment with study intervention before Visit 6 (Week 2).

Note: Participants who are unable to tolerate study intervention after a dose modification to the intended regimen should be discontinued from study intervention.

The participant begins to use a prohibited medication/therapy/product or a prohibited dose of an allowed medication listed in Section 8.1.7.2 (Concomitant Medications, Table 2). This criterion includes participants who test positive (local or central) for a drug of abuse (except cannabis, which is not prohibited if abuse or substance use disorder is ruled out).

Note: Participants who are willing and able to safely (per the investigator) stop using the prohibited medication/therapy/product (including drugs of abuse) or reduce from a prohibited to an acceptable dose for an allowed medication through Visit 9 (Post-dose Follow-up Visit) may continue study intervention at the investigator's discretion.

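### For a dosed participant with non-passive C-SSRS item 4/5 ideation or suicidal behavior, Section 7.1 stops drug but keeps follow-up, while Section 8.3.7.1 ends study participation

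*Combined protocol and SAP*

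**What the plan says.** Section 7.1 opens its list of mandatory stopping reasons with "A participant must be discontinued from study intervention but continue to be monitored in the study for any of the following reasons". One entry on that list begins "The participant reports suicidal ideation with intent, with or without a plan or method through an AE or C-SSRS", and it also covers suicidal behavior. The entry has an exception: if the ideation is passive, intent is denied and the participant is not judged at serious risk, then "the participant may continue on study intervention". More generally, 7.1 says that participants who stop drug early "will still continue to participate in the study as specified in Section 1.3 and Section 8.11.6", and that the visits and procedures in the Schedule of Activities (SoA) should be completed.

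Section 8.3.7.1 takes the same trigger, requires evaluation on the same day by a qualified mental health professional, and applies nearly the same exception. Here the exception decides something else: participants who, among other conditions, "are not judged to be at serious risk for self-harm during the course of the study may continue in the study". For the rest, "other participants must be discontinued from study participation and receive appropriate clinical follow-up care to ensure their safety".

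Section 7.1 points to 8.3.7.1 in these words: "Refer to Sections 8.3.7.1 on Clinical Assessments for Suicidal Ideation and Behavior Monitoring (for requirements pertaining to the evaluation of such events". Neither section says which governs what happens to the participant afterwards.

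**The concern.** The two instructions are both mandatory and differ for the same person. Under 7.1 the participant comes off drug and stays in the study. Under 8.3.7.1 the participant leaves the study. Section 7.2 says that someone who withdraws is no longer seen at scheduled protocol visits. Applying that to a removal ordered by the protocol is an inference, but the natural one.

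At stake is scheduled follow-up of the participants at highest suicide risk:

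- **C-SSRS.** Section 9.6.2 counts each participant by the most severe treatment-emergent event in the assessment period, so ending follow-up could miss later worsening.
- **Laboratory tests.** Section 4.3.2 added post-treatment laboratory monitoring after transaminase elevations in earlier studies. Section 2.2.2 describes one that appeared 2 weeks after a 4-week trial ended, in a participant whose assignment is still blinded.
- **Rating scales after drug is stopped.** The supplemental treatment-policy (TPS) analysis in Section 9.3.1 is meant to use these.

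**Working it through.** No plan figure bears on this point, so the check is a comparison of text followed by a count from the SoA.

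**1. Same trigger, different consequence.**

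| | Section 7.1 | Section 8.3.7.1 |
|---|---|---|
| Trigger | Item 4/5 ideation or suicidal behavior | Same |
| Exception (passive, denies intent, not at serious risk) | May stay on study intervention | May stay in the study |
| Everyone else | Stop drug, keep monitoring | Leave study participation, receive clinical care |

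**2. Can loose wording reconcile them?** If study participation in 8.3.7.1 meant only dosing, there would be no conflict. But that sentence sets it against continuing in the study, whereas the parallel exception in 7.1 speaks of continuing on study intervention. Section 7.1 also states that stopping drug is not withdrawal. The protocol uses these as separate concepts.

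**3. Which section is out of line?**
- Sections 8.1.16 and 8.11.6 encourage participants who stop drug to attend all remaining visits.
- Section 8.1.17 (unblinding) and Section 8.3.6.2 (positive pregnancy test) both stop drug and keep following the participant.
- The cross-reference in 7.1 sends the reader to 8.3.7.1 for evaluation, not disposition.

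All of these support the 7.1 model.

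**4. Scheduled assessments at stake per affected participant.** From the SoA after Visit 4: C-SSRS at Visits 5, 6, 7, 8, 9 and 10 (6); MADRS at Visits 5, 6, 7, 8 and 9 (5); chemistry/hematology at Visits 6, 8 and 10 (3). The count is the number of these visits still to come after the event. An early EOT/DC visit is not counted as lost: 8.11.5 expects it after stopping drug, and 8.1.16 encourages it on withdrawal. The documents do not say whether Visit 8 is still held after an early EOT/DC visit, so both counts are shown (C-SSRS / MADRS / chemistry-hematology).

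| Event time | Visit 8 still held | Visit 8 replaced (minus 1 each) |
|---|---|---|
| After first dose, before Visit 5 | 6 / 5 / 3 | 5 / 4 / 2 |
| Visit 5 to before Visit 6 | 5 / 4 / 3 | 4 / 3 / 2 |
| Visit 6 to before Visit 7 | 4 / 3 / 2 | 3 / 2 / 1 |
| Visit 7 to before Visit 8 | 3 / 2 / 2 | 2 / 1 / 1 |
| Visit 8 to before Visit 9 (treatment completed) | 2 / 1 / 1 | not applicable |
| Visit 9 to before Visit 10 | 1 / 0 / 1 | not applicable |

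These are maxima, because 7.1 says visits should be completed and 8.1.16 and 8.11.6 only encourage them.

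**5. Effect on the analyses.**
- Primary hypothetical-strategy (HS) analysis: Section 9.3.1 discards data after discontinuation of study intervention, and drug stops under either section. Values affected: 0.
- Supplemental TPS analysis: the Week 3 value (daily dose versus placebo) can be lost only for an event before Visit 7, and the Week 1 value (intermittent dose versus placebo) only for an event before Visit 5. Loss is possible rather than certain. The early EOT/DC visit includes a MADRS that may fall near Week 1 or Week 3, and the documents give no rule for assigning it to a week.

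**The case against.** The best defense is that 8.3.7.1 is a specific suicidality clause and may be a deliberate additional safety ground for removal. Section 7.2 lists withdrawal of consent as a mandatory reason to leave the study, but it does not say that this is the only one. That stands: the direction of the fix is an inference from the rest of the protocol, and the sponsor could choose otherwise. It does not remove the conflict, because 7.1 would then have to change.

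The consequence is also small. Drug stops under either section, and same-day evaluation, clinical care, recording as an event of clinical interest and adverse-event follow-up apply either way. This stands too, and it limits the point to scheduled follow-up and supplemental data.

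Three stronger readings are tempting, and the documents do not support them:

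- **That the removal rule applies at every stage of the study.** The time phrase belongs to a different sentence, which begins "Participants who at any time during this study report suicidal ideation or behavior that is considered to be an AE" and requires assessment by the investigator. The disposition sentence does not repeat it. Before randomization, exclusion criterion 11 already requires exclusion, so no conflict is shown there.
- **That 7.1 makes every remaining visit compulsory.** The wording is should be completed, or encouraged.
- **That the primary result is at risk, or that participants would go without care.** Neither follows, for the reasons above.

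**Conclusion.** The contradiction is real and is in the current text. For dosed participants with item 4/5 ideation not judged passive, or with suicidal behavior, the two sections give dispositions that cannot both be followed, and no text ranks them. The better-supported reading is that 8.3.7.1 should be aligned with 7.1.

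Its size is at most 6 C-SSRS, 5 MADRS and 3 chemistry/hematology assessments for one participant with an early event, and fewer for later events. No primary HS value is affected, and TPS values may be. The documents give no event rate, and criterion 11 screens out recent cases, so the number of participants is unknown and may be zero.

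The conclusion assumes that discontinuation from study participation ends scheduled visits, as 7.2 says of withdrawal. It should be corrected because conflicting mandatory instructions on suicidality in a depression trial should not be left to each site, even though the statistical effect is minor.

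**What to change.** In Section 8.3.7.1, for randomized and dosed participants:

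1. Make the passive-ideation exception govern staying on study intervention instead of staying in the study.
2. Replace removal from study participation with stopping study intervention, if it is still being taken, and continued monitoring in the study under Section 7.1. Keep the same-day evaluation and the clinical follow-up care.
3. Add that clinically needed treatment may start at once, including Table 2 therapies, changes to antidepressant therapy, and psychotherapy, whatever the restrictions to Visit 9 say.

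The third item is needed because keeping these participants in follow-up would otherwise leave them under inclusion criterion 6 (no new psychotherapy), Section 8.1.7.2 (stable antidepressant therapy) and, for treatment completers, Section 8.11.7 (no Table 2 therapy before Visit 9). Section 8.11.5 releases only Table 2 items, and only after an early EOT/DC visit. Section 6.5 leaves supportive therapy to the clinician, so care is not barred, but the rule should say so. The release costs the primary analysis nothing: those who stop drug early already have their later data discarded, and Visit 9 lies outside the Week 1 to Week 4 model in Section 9.6.1.

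Pre-randomization cases stay under criterion 11 and need no new rule. If the sponsor does intend removal from the study, 7.1 must be changed instead.

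The cost is two phrases and one added sentence in the next amendment, with a short clarification to sites. No visits, procedures or analyses are added.
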